Putra et al.⁶ reports that with low bone density, the drilling trajectory might deviate toward the softer part of the bone after the second drilling procedure. Therefore, highest deviation was found in the cases that the bone density was less than 500 Hounsfield unit (HU).

Multiple bone condition predictors like bone density, bone width, and cortical bone thickness significantly influenced the accuracy in implant placement with CGS.

Some other factors like implant site, type of implant (immediate, early or delay), mucosal thickness, graft in the area, quantity of implants have been reported as a factor influencing the accuracy of the guided surgery.^{6,7}

The aim of this cohort prospective study is to assess the influence of clinical and anatomical factors on the accuracy of computer-guided surgery. The following factors will be taken into consideration for the analysis of the data: 1) Implant location (anterior or posterior); 2) Single or multiple implants; 3) Mucosal thickness; 4) Native or regenerated bone, 5) immediate or delay implant.

2. Objectives.

Overall objective.

The aim of this cohort prospective study is to assess the influence of clinical and anatomical factors on the accuracy of computer-guided implant surgery on immediate and delayed implant placement:

Specific objectives:

- 1) To assess the influence of implant location (anterior or posterior) on the accuracy of CGS
- 2) To assess the influence of time for implant placement (immediate or delay) on the accuracy of CGS.
- 3) To assess the influence of type of bone (native or regenerated bone)
- 4) To assess the influence of bone density on the accuracy of CGS.

Hypothesis.

- 1: H1 implant location (anterior or posterior) has an influence on the accuracy of CGS
- 2: H1 The time for implant placement (immediate or delay) has an influence on the accuracy of CGS.
- 3: H0 The mucosal thickness does not have an influence on accuracy of CGS.
- 4: H1 The bone density has an influence on the accuracy of CGS.

Material and methods.

The study will be performed at a private practice (Blasi Dental Clinic) which is under the tutelage of the Universitat Internacional de Catalunya (UIC) CElm.

Moreover, the present study will be registered in clinicaltrials.gov.

For the sample size calculation, we use as reference Putra's¹⁴ article where it is reported correlations between different deflection parameters and bone density. These are weak-moderate magnitude correlations (0.3<r<0.5).

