The sample size was calculated for 3 levels of statistical power, a 95% confidence level with Pearson's linear correlation coefficient null test)

Degree of correlation Power reached

	70%	80%	90%
r=0.3 (weak)	67	84	112
r=0.5 (moderate)	23	29	37

To detect a weak magnitude correlation as significant, 84 patients will be needed for this study.

Inclusion criteria.

- Patients between 25 to 60 years old.
- Periodontally stable patients. Adequate oral hygiene with less than 15% Full Mouth Plaque Score (FMPS).
- Patients who need dental implant treatment without simultaneous regeneration.
- Ability to follow instructions and availability to attend for regular compliance during the entire study.
- With presence of partial edentulism (at least 6 remaining teeth distributed in the dental arch to support the guide).

Exclusion criteria:

- Active infections

- Untreated periodontal disease
- Heavy smokers (>10 cigarettes per day)
- Drug / Alcohol dependency
- Medical condition contraindicating implants dependency
- Patients under bisphosphonate therapy
- Limited mouth opening

All the information will be given to the patients before sign and obtain the informed consent form.

Clinical procedures.

After assessing the fulfillment of the inclusion criteria, pre-operative cone beam computed tomography (CBCT) (Newtom, Cefla S.C.) and intraoral digital impressions (Trios®, 3Shape Dental Systems, Denmark) will be obtained for each patient to achieve a digital wax-up and a presurgical plan for the exact position of the implants by a single calibrated operator (RP).

Every patient could have a maximum of four implants to be placed (one per quadrant), in those cases, there will be one guide per implant.

The digital imaging and communications in medicine (DICOM) files will be imported to a guided-surgery planning software (Codiagnostix, Dental wings) to perform an implant planning based on the digital wax up; in this step the assessment of the mucosal thickness will be performed using the STL and the DICOM files superimposed. The measurement will be taken from the crestal bone until the soft tissue surface (mm).

Furthermore, a surgical guide will be designed, and 3D printed (SprintRay Pro S; SprintRay Inc) with implant guide resin (SprintRay EU Surgical Guide Clear; SprintRay Inc) by RP for the surgical procedure, supported by the whole dental arch, and reinforced with one bar across the arch.

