Through guided surgery, previously planned and designed based on CBCT study and CAD/CAM scanning, placement of Conelog Progressive line implants

(Biohorizons Camlog, Iberia) will be performed in maxilla or mandibula in a one stage surgery by a 8 years' experience operator (GB).

Implant placement will be fully guided and a postoperative CBCT in ECO mode ($35\mu\text{Sv}$) will be taken after the implant placement to assess the final position.

Both CBCT will be aligned (pre-op scan and post-op scan) to make calculations by a single evaluator (AB) included the following (Fig. 1): (1) angle: angle deviation measured in degrees; (2) base: deviation at implant shoulder in millimeters; (3) tip: deviation at implant apex in millimeters; (4) 3D offset: global deviation in 3D directions in millimeters; (5) mesiodistal deviation in millimeters: (+) deviated to the distal direction and (-) deviated to the mesial direction; (6) buccolingual deviation in millimeters: direction: (+) deviated to lingual direction and (-) deviated to buccal direction; and (7) apicocoronal deviation in millimeters: direction: (+) deviated in the apical direction. and (-) deviated in the coronal direction.

[figure not shown]

Figure 1. Parameters to evaluate de position of the implant. ¹⁴

Clinical and study schedule

The estimated appointments for all patients:

- Screening visit: Selection, recruitment of patients, and signing of informed consent.
- First visit: Data collection (intraoral scanning and CBCT acquiring).
- Second visit: Implant placement and post-operative CBCT.

Ethics

This protocol follows the ethical principles regarding human experimentation recommended by the World Medical Association in the Declaration of Helsinki.

After fulfilling the inclusion criteria, all patients will receive a full informed consent.

After evaluation and clarification of possible concerns, the patient will return the signed consent as an agreement of participation.

Statistical analysis.

A descriptive analysis will perform by analyzing the mean, standard deviation, minimum, maximum values, and median for each outcome. For a 95% confidence level and an estimated standard deviation, T-test and Pearson's linear correlation coefficient null test will be used to analyze the data.

Study limitations

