This clinical study presents some limitations to be taken into considerations. First, if the surgical guide could not fit properly, present movements or break during the procedures, Second, the need of taking two CBCT in one month can represent a topic to be aware. And finally, the data should permit the correct alignment for further analysis and evaluation and its quality must be enough to facilitate the data analysis.

Contingency plan.

Rewarding the mishap of the fitting of the guide, in those cases we will print two guides per case, to have a backup if the first guide breaks. If the guides are not fitting properly, the patient should be excluded from the study.

[figure not shown]
For this study we will use the ECO mode which only presents a minimum effective dose of 9 μ Sv (four times less radiation than a regular CBCT and almost the same radiation as an orthopantomography)

Moreover, if any of the data collected presents any error that could interfere in the data analysis, the patient will be excluded for the study.

Annexes

- a. Flow chart
- b. Patient data collection
- c. Timeline

a. Flow chart

b. Data collection

PATIENT DATA COLLECTION	
PATIENTS PRE-SURGICAL INFORMATION	
Patient number: _____	
Age: _____	
Sex: _____	
Medical conditions _____	
Allergies: _____	
Smoker: Yes _____ No _____ How many per day? _____	
Site of implant placement: _____	
Immediate implant? Yes _____ No _____	
Native bone? Yes _____ No _____	
Single or multiple implants? _____	
Mucosal Thickness (millimeters) _____	
Bone Density (Hounsfield units) _____	
Complications with the surgical guide? Yes _____ No _____	
Other complications _____	

c. Timeline of study

Glosario de términos.

- 1. Computer-guided surgery (CGS)**
- 2. Cone beam computed tomography (CBCT).**
- 3. 3-Dimensional (3D)**
- 4. Hounsfield unit (HU).**
- 5. Full Mouth Plaque Score (FMPS).**

Investigador Principal [name]

Fdo: [name]

IP or tutor signature

Supporting researcher:

--	--

2.

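### Both contingency rules exclude the whole patient, so when a problem is confined to one implant site the patient's sound implants are discarded as well

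*Combined protocol and SAP*

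**What the plan says.** The Contingency plan has two exclusion rules. On guide fit: "If the guides are not fitting properly, the patient should be excluded from the study". On data: "if any of the data collected presents any error that could interfere in the data analysis, the patient will be excluded for the study". Both name the patient as the unit removed. The first follows the statement that "we will print two guides per case, to have a backup if the first guide breaks".

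Clinical procedures states: "Every patient could have a maximum of four implants to be placed (one per quadrant), in those cases, there will be one guide per implant". Each guide is "supported by the whole dental arch, and reinforced with one bar across the arch". For measurement, "Both CBCT will be aligned (pre-op scan and post-op scan) to make calculations by a single evaluator", and the outcomes include "2) base: deviation at implant shoulder in millimeters; (3) tip: deviation at implant apex in millimeters", which are properties of a single implant.

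The Introduction lists "2) Single or multiple implants" among five factors to be analysed; it is not one of the four specific objectives. The sample size is 84 patients, with no stated allowance for exclusions. Annex b (Data collection) is headed by patient and shows a single entry each for site, immediate placement, native bone, mucosal thickness, bone density and guide complications. No section provides for excluding one implant while keeping the patient's others.

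**The concern.** The unit excluded (patient) is larger than the unit in which a problem can arise and on which accuracy is measured (implant). If one guide of several does not fit, or one site's measurement is unusable, the text also removes the implants whose own guide and data are sound. A single-implant patient has no other implant to lose. A multiple-implant patient has more chances to trigger a rule and loses more when that happens.

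What is at stake is usable data in a sample planned without a margin, lost unevenly across the levels of a factor that the Introduction lists for analysis. If a guide complication is not tied to its implant when it occurs, the sound implants may be hard to identify later.

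**Working it through.** **The plan's own figure.** For r = 0.3, 80% power and two-sided 5%, Fisher's z gives n = ((1.96 + 0.842)/atanh(0.3))² + 3 = 84.9, against 84 stated. The planned size is reproduced to within one patient; this point does not depend on it.

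**Inputs from the documents.** Implants per patient k = 1 to 4; one guide per implant; 84 patients; unit excluded = patient.

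**Inputs assumed, because the documents give none.** Failure probability per site p (2%, 5%, 10%); dependence between a patient's sites, as an exchangeable Gaussian latent variable with correlation ρ; the number of patients with several implants.

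**Formulas.** Let S(k) be the probability that none of k sites fails; with independent sites S(k) = (1 − p)^k, otherwise it is found by numerical integration.
- Patients removed under the present rule: 1 − S(k).
- Share of sound implants discarded: 1 − S(k)/(1 − p).

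**Results at p = 5%** (one-implant patients: 5.0% removed, no sound implant lost, in every row):

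| ρ | Removed, k = 2 | Removed, k = 4 | Sound implants discarded, k = 2 / 3 / 4 |
|---|---|---|---|
| 0 | 9.8% | 18.5% | 5.0 / 9.8 / 14.3% |
| 0.5 | 8.8% | 14.4% | 4.0 / 7.2 / 9.9% |
| 0.8 | 7.5% | 10.6% | 2.7 / 4.5 / 5.9% |
| 1 | 5.0% | 5.0% | 0 / 0 / 0% |

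At k = 4, removal for ρ = 0 / 0.8 / 1 is 7.8 / 4.7 / 2.0% at p = 2% and 34.4 / 19.3 / 10.0% at p = 10%. If ρ = 0.8 holds only within an arch, with two implants per arch and independent arches, then at p = 5% and k = 4 the rule removes 14.5% of patients and discards 10.0% of sound implants.

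**In 84 patients at p = 5%**, the others having one implant each:
- 21 patients with two implants (63 + 42 = 105 implants). Sound implants lost: 21 × 2 × 0.95 × 0.05 = 2.0 at ρ = 0, and 21 × 2 × 0.95 × 0.027 = 1.1 at ρ = 0.8.
- 21 patients with four implants (63 + 84 = 147 implants). Sound implants lost: 21 × 4 × 0.95 × 0.143 = 11.4 at ρ = 0, and 21 × 4 × 0.95 × 0.059 = 4.7 at ρ = 0.8.

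**Power on patients retained**, r = 0.3, as Φ(atanh(0.3)·√(n − 3) − 1.96). In the two-implant example at ρ = 0, the present rule keeps 63 × 0.95 + 21 × 0.9025 = 78.8 patients (76.9%). An implant-level rule loses a patient only if every site fails and keeps 63 × 0.95 + 21 × 0.9975 = 80.8 (77.9%). At ρ = 0.8 it is 79.3 against 80.3 patients (77.1% against 77.7%). In the four-implant example the same sum gives 76.9 against 80.8 patients at ρ = 0 (75.9% against 78.0%), and 78.6 against 80.6 at ρ = 0.8 (76.8% against 77.8%).

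**Bias check.** Simulation with misfit correlated 0.3–0.5 with deviation, mean of retained implants, four-implant against one-implant patients: 0.00 SD at ρ = 0 and ρ = 1. At ρ = 0.3–0.8 it is 0.02–0.06 SD lower for p = 5–10%, and 0.01–0.02 SD lower for p = 2%.

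**The case against.** The strongest case against is that failures are largely shared. The data rule answers the limitation, under Study limitations, that the data must permit correct alignment. One pre-operative and one post-operative scan are aligned per patient, so most such failures affect every implant and an implant-level rule saves nothing. Guides come from the same patient's scans and rest on the whole arch, and the plural in the misfit rule, after two guides per case, may mean that both guide and backup fail. This stands in part and lowers the plausible size. It does not remove the point: the data rule covers any collected item, which can include one site's thickness or density, and guides on the upper and lower arch rest on different teeth.

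Second, the analysis unit is not stated. If one implant per patient were analysed, much of the discarded data would not have been used. If all are analysed, keeping more implants per patient adds clustering that the planned t-test and Pearson test ignore. Both remarks are fair; the second belongs in the fix.

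Third, the form might be completed once per implant; nothing forbids it. That stands: it is an inference, not a fact, that complications cannot be traced to an implant, and it would apply equally to every site-level item.

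A reader might infer that the rules bias the single-versus-multiple comparison. The documents do not support that. They give no failure rate and no link between misfit and deviation, the comparison is not a numbered objective, and the modelled shift is zero to small. A reader might also infer that implants placed with a guide complication should stay in the main analysis. That could reverse the plan's misfit exclusion rather than change its unit, and nothing here argues for it.

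**Conclusion.** The point holds as a mismatch of units. Both rules remove the patient where the affected unit may be one implant, and no section allows the sound implants to be kept. That part rests on the text alone.

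The size rests on assumption. At 5% failure per site, the two 84-patient examples lose about 1–2 of 105 implants or about 5–11 of 147 (ρ from 0.8 to 0), and none at full dependence. On patients retained, the cost is about one point of power or less in the two-implant example and about one to two points in the four-implant example, which supposes that a quarter of patients reach the protocol's maximum. It is a modest, avoidable loss of precision and not a demonstrated bias. The change is a cheap improvement, best made before data collection is complete.

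**What to change.** In both Contingency plan sentences, change the unit excluded from the analysis from the patient to the affected implant:
- Exclude an implant whose own guide meets the plan's misfit criterion, or whose own data cannot be aligned or read. Keep the patient's other implants.
- If a shared scan fails, exclude every implant it affects.
- Make and record each exclusion before deviations are calculated, and report exclusions by factor level.
- State whether the plural in the misfit rule means the guide alone or the guide and its backup.
- Complete all site-level form items (site, immediate placement, native bone, mucosal thickness, bone density, guide complication) once per implant.
- Where more than one implant per patient is analysed, use a method that allows for clustering within the patient.

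The misfit criterion itself is not changed, and clinical handling of a guide that does not fit stays with the investigators. The cost is slightly more form-filling and analysis work, with no extra patients, visits or scans.

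### The data-error rule removes the whole patient for any interfering error, with no correction step, no limit to the affected reading or implant, and no requirement to decide before the deviation is calculated

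*Combined protocol and SAP*

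**What the plan says.** The rule is in the Contingency plan: "if any of the data collected presents any error that could interfere in the data analysis, the patient will be excluded for the study". It answers a limitation stated under Study limitations, that "the data should permit the correct alignment for further analysis and evaluation and its quality must be enough to facilitate the data analysis". Neither sentence defines an error, sets a quality threshold, names who decides, or says when.

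Four other places bear on it:

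- **Outcome measurement (Clinical procedures).** A post-operative CBCT "will be taken after the implant placement to assess the final position", and "Both CBCT will be aligned (pre-op scan and post-op scan) to make calculations by a single evaluator". Seven deviation measures follow, three of them signed. No blinding, second reader or acceptance step is described.
- **Implants per patient (Clinical procedures).** A patient may receive up to four implants, each with its own guide.
- **Sample size (Material and methods).** 84 patients, for a correlation of 0.3 at 80% power and 95% confidence, with no addition for exclusions.
- **Statistical analysis.** After descriptive statistics (mean, SD, minimum, maximum, median), "T-test and Pearson's linear correlation coefficient null test will be used to analyze the data". There is no analysis set, missing-data rule, outlier rule or sensitivity analysis.

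The Contingency plan also has a separate exclusion for guides that do not fit. This point does not depend on it.

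**The concern.** Three features of the rule cause trouble.

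1. **No correction step.** Mucosal thickness is read from superimposed STL and DICOM files, bone density is a Hounsfield value on the data form, and the deviations come from two digital scans. As long as the files are kept, a misreading can be re-read and a poor alignment repeated. The rule names neither option.
2. **The loss is larger than the error.** One faulty reading removes the patient. For a patient with four implants, a fault in one record would discard three sound ones, along with every other variable for that patient.
3. **No fixed time for the decision.** An error in the outcome data can be found only once the post-operative scan exists, and nothing requires the decision to come before the deviation is calculated. Deviation is the outcome of the study, so an exclusion influenced by it is selection on the outcome. If large deviations were queried more often than small ones, reported accuracy would look better than it was and associations with the factors would be weakened. Nothing in the Statistical analysis section would reveal this.

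**Working it through.** **Inputs.** From the documents: n = 84, r = 0.3, 95% confidence, mean apex deviation 1.4 mm with a range of 1.28 to 1.58 mm (Introduction). Assumed, because not given: a two-sided test, the exclusion rates, the SD of the deviation, and one value per patient.

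**1. The plan's own figure.** Fisher's z gives n = ((z₀.₉₇₅ + z₀.₈₀)/atanh(r))² + 3.

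- Uncorrected: ((1.960 + 0.842)/0.3095)² + 3 = 84.9, or 85 rounded up.
- With the bias correction r/(2(n−1)) added to atanh(r): 84.
- The corrected formula matches all six cells of the protocol's table (67/84/112 and 23/29/37). A one-sided test gives 68 for the same cell, so the two-sided reading is right.

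The powers below use the uncorrected form, power = Φ(atanh(r)·√(n−3) − 1.960). At n = 84 and r = 0.30 it gives 79.6%.

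**2. Loss unrelated to the outcome.** Removing about 5% (4 of 84) leaves n = 80 with r unchanged: 0.3095 × √77 − 1.960 = 0.756, so power is 77.5%.

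**3. Worst case: exactly the largest 5% of a one-sided, normally distributed deviation are removed.**

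- Cut-point c = 1.645, and φ(c)/0.95 = 0.1086. The mean falls by 0.11 SD.
- Remaining variance: v = 1 − 1.645 × 0.1086 − 0.1086² = 0.810.
- Correlation: r′ = 0.3√v / √(0.09v + 0.91) = 0.2699/0.9914 = 0.272.
- Power at n = 80: 0.279 × √77 − 1.960 = 0.488, or 69%.

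The same steps for the largest 2% (2 of 84, n = 82) give r′ = 0.285 and power 74%.

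**4. Half-selective case: 5% removed, half from the top 5% and half at random from the rest.** Half of the tail and 1 − 0.025/0.95 = 0.974 of the rest are kept.

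- The mean falls by 0.103 × (0.974 − 0.5)/0.95 = 0.05 SD, and v = 0.913.
- r′ = 0.2866/0.9961 = 0.288, and power at n = 80 is 74%.

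| Exclusions | n | r | Power | Fall in mean |
|---|---|---|---|---|
| None | 84 | 0.300 | 79.6% | 0 |
| 5% at random | 80 | 0.300 | 77.5% | 0 |
| 5%, half from the top tail | 80 | 0.288 | 74% | 0.05 SD |
| Largest 2% | 82 | 0.285 | 74% | 0.05 SD |
| Largest 5% | 80 | 0.272 | 69% | 0.11 SD |

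**5. Check with a skewed outcome.** In 4,000 simulated trials of 84 patients, apex deviation followed a gamma distribution with mean 1.4 mm and an assumed SD of 0.5 or 0.7 mm, and was correlated −0.3 with bone density. Removing the four largest values moved the mean from 1.40 to 1.34 or 1.31 mm, the average maximum from 2.9 or 3.7 to 2.3 or 2.7 mm, the mean observed r from −0.29 to −0.27, and power from about 79% to 68%. This agrees with step 3.

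**The case against.** The strongest reply is that the rule is aimed at unusable images. It follows a limitation about alignment and image quality, and it does not forbid correction: an error that has been put right no longer interferes with anything. On that reading the sentence is loosely worded and nothing more. The intent is probably as described. However, the sentence covers any collected data, names exclusion of the patient as the only action, and sets no threshold. Two people applying it could reasonably reach different datasets.

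A reader might go further and infer that the evaluator would discard large deviations as alignment errors because the two cannot be told apart. The documents do not support this:

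- They do not say who decides exclusions. That it would be the evaluator is an inference.
- Alignment comes before the calculations. The pre-operative scan is taken a visit before placement and holds no study implant, so the scans must be matched on anatomy. Inclusion requires at least six teeth distributed in the arch. Alignment can therefore be judged without looking at the implant.
- Nothing directs anyone to drop extreme results.

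It is also fair to say that the worst case is a ceiling, since it removes the whole upper tail and nothing else. It fits the one-sided measures. For the three signed measures, extremes lie in both tails, and losing them need not shift the mean. Even at the ceiling, the mean apex deviation moves by 0.06 to 0.09 mm under the assumed SDs, against a cited range of 1.28 to 1.58 mm.

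**Conclusion.** The point holds as a defect in a stated rule. Whole-patient exclusion without a correction step follows from the wording, and so does the loss of sound implants when one record is faulty. Selection on the outcome is something the rule leaves room for; it is not something the plan prescribes or makes likely.

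The effect on power runs from about 2 percentage points for a random 5% loss (79.6% to 77.5%) to about 11 points in the worst case (to 69%), with about 74% if half the exclusions come from the upper tail. The mean is understated by 0 to 0.11 SD over the same range. These figures rest on r = 0.3, one normally distributed value per patient, a one-sided deviation measure and an assumed 5% exclusion rate, which the documents do not supply. The rule should be changed, but it does not undermine the design.

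**What to change.** Replace the sentence in the Contingency plan with:

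> Errors are first corrected by repeating the reading or the alignment from the stored DICOM/STL files. Adequacy of alignment is judged on teeth and bone surfaces and recorded as accept or reject before any deviation is calculated. If an error cannot be corrected, only the affected variable or implant is set to missing, not the whole patient. If a registration failure is found after the deviation has been calculated, the alignment is repeated using the same anatomical criterion; any value still removed is logged with its reason, original deviation and factor values, and the analysis is repeated with it included. All exclusions are reported.

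A flat ban on removal once the deviation is known would be simpler, but it would keep genuine registration failures found late. Setting values to missing with no safeguard on timing would leave the present opening. The log and the repeated analysis deal with both.

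The cost is protocol wording, one accept/reject field, a few repeat alignments and a short log. No extra reader or scan is needed.
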